3.1.2 Secondary

- I. To evaluate improvement of symptoms using CAT score after 3 and 6 months.
- II. To evaluate improvement of lung function (using spirometry) and exercise capacity (using 6MWT) after 3 and 6 months.
- III. To evaluate moderate and severe exacerbation rates after Aerobika® OPEP device usage in 3 and 6 months.

3.2 Significance of Research

Aerobika® OPEP device is an alternative non-pharmacological therapy to improve patient's symptoms, quality of life, reduce exacerbation and hospitalization, thus will reduce cost of treatment in a long run.

CHAPTER 4

RESEARCH METHODOLOGY

4.1 Type of Study

This is a single center, prospective, interventional study of COPD patients who are under follow up of Respiratory Unit Universiti Kebangsaan Malaysia Medical Center (UKMMC). All patients involved in the study will be given Aerobika® OPEP on top of standard care of COPD.

4.2 Study Design

4.2.1 Period of Study

The study will be conducted from June 2021 to November 2022 after receiving approval by the research ethics committee.

4.2.2 Study Setting

The study will be conducted in the Respiratory Unit, Department of Internal Medicine of Universiti Kebangsaan Malaysia Medical Centre (UKMMC).

4.2.3 Sampling Population

This study will include patients diagnosed with COPD GOLD 2-4 attending the respiratory outpatient clinic UKMMC from June 2021 until November 2022. Demographic and clinical data will be collected. Patient will be followed-up at 3 and 6 months after intervention.

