3.1 Objectives

3.1.1 Primary

To demonstrate improvement of small airway parameter using IOS after introduction of Aerobika® OPEP in 3 and 6 months among COPD patients in UKMMC.

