4.3 Study Protocol and Data Acquisition

This is a prospective interventional study conducted on COPD patients (GOLD 2-4) under the Respiratory Unit, Department of Internal Medicine in UKMMC, who qualified both the inclusion and exclusion criteria. Beforehand, all potential subjects will undergo screening and survey to exclude any possible symptoms of COVID-19 disease. All eligible patients will be briefed about this study.

Subsequently, consent will be obtained from those who are agree to participate, either from the patient him/herself or their next-of-kin. The process of briefing and obtaining consent will be only done once the patient is stable. These processes will not in any way interfering with clinical evaluation, investigation, treatment and intervention done to the patient by the attending doctor. All of the consented patients will be given Aerobika® OPEP.

Prior to the initiation of Aerobika® OPEP device, baseline of IOS parameters, symptoms (using CAT score), lung function (using spirometry-FEV₁ and FVC), exercise capacity (using 6MWT) and exacerbation episodes of the past 6 months will be done and recorded in data collection sheet. All recruited patients will receive OPEP and trained to use for 10 minutes, 2 times per day ⁽³²⁾. Patients also will be emphasized that standard care for COPD management will be continued. An adherence sheet will also be provided to patients at which they can put crosses when they use the device as advised. They are encouraged to use Aerobika® immediately after using their inhalers in order to increase adherence of treatment.

Patients will be given phone call 2 days after they received Aerobika® as a reminder and also to ensure they are using it in a correct way. At week 12 and week 24 of Aerobika® OPEP usage, their IOS parameters, symptoms (using CAT score), lung function (using spirometry-FEV₁ and FVC), exercise capacity (using 6MWT) and exacerbation episodes will be reassessed. During clinic visit also, his/her standard management for COPD will be checked to ensure no change in the inhaler regime. Within the study period of 6 months, patient will be given follow-up phone calls every two to three weeks to ensure their adherence toward Aerobika®.

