R5-R20 (cm/H ₂ O/L/sec)			

CHAPTER 10
GANTT CHART

	November 2020- January 2021	January 2021	January 2021- June 2021	June 2021- November 2022	November 2022- January 2023	January 2023- April 2023	April 2023- May 2023
Literature review							
Proposal correction, submission and presentation							
Ethics Committee Approval							
Recruitment of study subjects							
Data entry and analysis							
Writing report and thesis submission							
Thesis presentation							

CHAPTER 11
APPENDICES

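### Sections 4.2.1 and 4.2.3 give one window for the whole study and for patient entry, with no last-enrolment date, so late entrants have no week-24 assessment within the stated period

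*Combined protocol and SAP*

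**What the plan says.** Section 4.2.1 sets the calendar: "The study will be conducted from June 2021 to November 2022". Section 4.2.3 draws the sample from patients "attending the respiratory outpatient clinic UKMMC from June 2021 until November 2022" and adds: "Patient will be followed-up at 3 and 6 months after intervention". Section 4.3 fixes the visits: "At week 12 and week 24 of Aerobika® OPEP usage, their IOS parameters" and the other outcomes are measured again. The primary objective (3.1.1) is "improvement of small airway parameter using IOS after introduction of Aerobika® OPEP in 3 and 6 months".

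The Gantt chart in Chapter 10 lists seven activities and seven periods. "Recruitment of study subjects" is the fourth activity, and the fourth period is June 2021 to November 2022. "Data entry and analysis" is the fifth, and the fifth period is "November 2022- January 2023". No row is given to follow-up. The cell shading is not in the text available for review, so this pairing rests on row and column order.

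Section 4.5 asks for 34 patients (effect size 0.5, 80% power, 5% significance), raises this by 40% to a minimum of 48 to cover withdrawal, dropout and missing data, and aims for 60 because 60 devices were donated.

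**The concern.** If patients may enter until the month in which the study ends, those who enter in the last 24 weeks have no 6-month value, and those who enter in the last 12 weeks have no 3-month value either. Both are time points of the primary objective. These values would be missing because of the calendar, whatever the patients do. The 40% allowance was not described as covering that, yet it is the only reserve. Ordinary attrition draws on the same reserve, including the rule in section 4.2.5 that a patient whose inhaler changes is dropped. The plan has no rule for patients who have not reached week 24 when data collection closes.

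**Working it through.** **The plan's own sample size.** For a two-sided 5% paired t-test with 80% power and d = 0.5, ((1.960 + 0.842)/0.5)² = 31.4. The small-sample term 1.960²/2 = 1.9 brings this to 33.3, so 34. Exact power is 80.8% at n = 34 and 79.5% at n = 33. Inflation: 34 × 1.4 = 47.6, so 48. Both stated figures reproduce. The reserve is 48 − 34 = 14 patients, or 29% of 48; at 60 it is 26.

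**Cut-off dates.** Take the study period as 1 June 2021 to 30 November 2022, which is 548 days.
- Week 24: 30 November 2022 − 168 days = 15 June 2022.
- Week 12: 30 November 2022 − 84 days = 7 September 2022.
- A patient entered on 30 November 2022 reaches week 24 on 17 May 2023.

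**Share affected.** The documents give no accrual rate. Two cases show the range.
- All patients entered by 15 June 2022: no loss.
- Even accrual over the 548 days (an assumption), with visits ending on 30 November 2022: 168/548 = 30.7% lack week 24 and 84/548 = 15.3% lack week 12.

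Under even accrual, before any dropout:

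| Enrolled | Can have week 24 | Can have week 12 |
|---|---|---|
| 48 | 48 × 0.693 = 33.3 | 48 × 0.847 = 40.6 |
| 60 | 60 × 0.693 = 41.6 | 60 × 0.847 = 50.8 |

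At 48, the calendar removes 48 × 0.307 = 14.7 patients against a reserve of 14. At 60 it removes 18.4 against 26, and the remaining 41.6 could lose 1 − 34/41.6 = 18% before falling to 34.

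**Adding ordinary dropout at week 24** (rates assumed, numbers rounded down):

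| Enrolled | Other dropout | Left at week 24 | Power | Power without the calendar loss |
|---|---|---|---|---|
| 48 | 0% | 33 | 79.5% | 92.4% |
| 48 | 20% | 26 | 69% | 85% |
| 48 | 29% | 23 | 63% | 81% |
| 60 | 0% | 41 | 88% | 97% |
| 60 | 20% | 33 | 79.5% | 92% |
| 60 | 29% | 29 | 74% | 89% |

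**If visits ran on to 31 January 2023**, overlapping data entry and analysis, the week-24 cut-off would move to 16 August 2022 and 106/548 = 19% would still be affected. The documents do not provide for this.

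**The case against.** The strongest reply is that the 18-month window was meant to hold about 12 months of entry and 6 months of follow-up. Nothing says that the last patient enters in November 2022. Enrolment is limited by the 60 donated devices, and the budget of 180 filters, mouthpieces and technician payments equals 60 patients × 3 visits, so every patient was expected to complete week 24. If the devices are all issued by mid-June 2022, every section can be followed. This stands as far as it goes: the budget shows that full follow-up was intended. It does not supply the missing date, because section 4.2.3 states entry over the full window and no section stops it earlier.

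The Gantt evidence is limited. With the shading lost, a reader might infer that analysis certainly begins in the month recruitment ends; row and column order suggests this but does not prove it. The recruitment row may also stand for all fieldwork. The data collection pathway in section 4.6 is not visible either. The point therefore rests on sections 4.2.1, 4.2.3 and 4.3, with the Gantt chart only agreeing.

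A reader might also infer that the trial will miss its 80% power. The documents do not support that. It requires accrual spread to the end of the window and visits stopping on 30 November 2022. Even then, before dropout, the shortfall at 48 is 33 against 34 patients, or 79.5% against 80.8%. The lower figures need further assumed dropout, and the plan aims for 60. The 3-month part of the primary objective is much less exposed.

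**Conclusion.** The concern holds as an unreconciled calendar with a conditional cost. Followed literally, the stated entry window and study period leave patients entered after about 15 June 2022 without a week-24 value, and those entered after about 7 September 2022 without a week-12 value. That much is date arithmetic and needs only the assumption that the period ends on 30 November 2022.

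The cost ranges from nothing, if entry is complete by mid-June 2022, to about 31% of patients at week 24 under even accrual. In the latter case the whole allowance behind the minimum of 48 is spent before anyone drops out, while a target of 60 keeps a margin of about 18%. The 31% is an illustration and not a forecast. The point should be fixed because it touches a primary time point and the plan does not control it, but it does not show that the study is underpowered.

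**What to change.** Separate accrual from follow-up in sections 4.2.1 and 4.2.3 and in the Gantt chart, and add a follow-up row. Then choose one of these:

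- **(a) Set a last-enrolment date** 24 weeks plus the visit window before data collection ends: 15 June 2022 or earlier if it ends on 30 November 2022. The date alone does not restore the numbers. At the even rate, 380/548 of the target is in by then, which is again 33 of 48 or 42 of 60. Recruiting 48 to 60 patients in about 12.5 months needs accrual 548/380 = 1.44 times as fast, so the plan should say how that will be achieved and tie the date to the number needed.
- **(b) Keep enrolling to November 2022**, complete week-24 visits to mid-May 2023 and start the analysis after that. This keeps the numbers and delays analysis and thesis by about 5 to 6 months.

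If neither is possible, restate the expected number and power at week 24, with the accrual assumption shown. Option (a) costs date changes and faster recruitment, option (b) costs time, and the last costs a revised paragraph in section 4.5. None needs patients or tests beyond those already planned.

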4.2.4 Inclusion Criteria

- I. Age 40 years or older
- II. COPD diagnosed according to the GOLD guidelines: GOLD 2 - GOLD 4
- III. Stable COPD patients with mucus hyperproduction: coughed and brought up sputum “several days a week” (>2 days a week) or “almost every day” in the month prior to the study ⁽²⁵⁾
- IV. Patients who can perform IOS
- V. Patients who can perform spirometry

- VI. Patients who can perform 6MWT
- VII. Patients with small air disease as measured by IOS ($R5-R20 > 0.71 \text{ cmH}_2\text{O/L/sec}$)

4.2.5 Exclusion Criteria

- I. COPD diagnosed according to the GOLD guidelines: GOLD 1
- II. Diagnosis of other chronic lung diseases: Asthma, Asthma-COPD Overlap, Interstitial Lung Disease, Bronchiectasis, Lung Cancer
- III. Patients with contraindication for spirometry: recent cardiac complications, major surgery ⁽³⁶⁾, severe advanced respiratory disease, or those with cognitively or neurologically impairment ⁽³⁷⁾
- IV. Patients not recommended for OPEP: neuromuscular weakness, recent facial, oral or skull surgery or trauma, recent oesophageal surgery, active haemoptysis, acute sinusitis, untreated pneumothorax, known or suspected tympanic membrane rupture or other middle ear pathology, overt right-sided heart failure ⁽²³⁾
- V. Patients with contraindication for 6MWT (**Table 1**)
- VI. Patient unable or unwilling to give informed consent
- VII. Change of inhaler during study period (will be dropped out from study)

Absolute and relative contraindications for field walking tests

Absolute	Relative
Acute myocardial infarction (3–5 days)	Left main coronary stenosis or its equivalent
Unstable angina	Moderate stenotic valvular heart disease
Uncontrolled arrhythmias causing symptoms or hemodynamic compromise	Severe untreated arterial hypertension at rest (200 mmHg systolic, 120 mmHg diastolic)
Syncope	Tachyarrhythmias or bradyarrhythmias
Active endocarditis	High-degree atrioventricular block
Acute myocarditis or pericarditis	Hypertrophic cardiomyopathy
Symptomatic severe aortic stenosis	Significant pulmonary hypertension
Uncontrolled heart failure	Advanced or complicated pregnancy
Acute pulmonary embolus or pulmonary infarction	Electrolyte abnormalities
Thrombosis of lower extremities	Orthopedic impairment that prevents walking
Suspected dissecting aneurysm	
Uncontrolled asthma	
Pulmonary oedema	
Room air S_{pO_2} at rest $\leq 85\%$ [#]	
Acute respiratory failure	
Acute noncardiopulmonary disorder that may affect exercise performance or be aggravated by exercise (i.e. infection, renal failure, thyrotoxicosis)	
Mental impairment leading to inability to cooperate	

Table 1: Absolute and relative contraindications for field walking tests ⁽³⁸⁾

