IOS is a simple, non-invasive method requiring only passive patient cooperation without special manoeuvre for evaluation of lung function through the measurement of both airway resistance and airway reactance.⁽¹⁵⁾ The pressure-flow oscillations are applied at the mouth superimposed on the subject's tidal breaths to measure respiratory system resistance and reactance at different oscillation frequencies. It uses sound waves to rapidly detect airway changes. When analysed, these pressure signals separately quantify the degree of obstruction in the central and peripheral airways ⁽¹⁵⁾. In IOS, it enables measurement of total respiratory resistance (R5) and proximal respiratory resistance (R20), with the R5-R20 difference reflecting small airway resistance ^(16,17). Small airway disease is significant if $R5-R20 > 0.71$ cmH₂O/L/sec ⁽¹⁷⁻²⁰⁾.

Treatment of COPD requires combination of pharmacological and non-pharmacological approaches. In non-pharmacological treatment, chest physiotherapy and pulmonary rehabilitation is the cornerstone of management of COPD patients. It can result in improvement of symptoms, increased exercise capacity, and improvement in lung functions ⁽²¹⁾. By early detection of SAD in COPD, it enables the physician to offer patients with a more targeted approach therapy, for example the use of small particle size inhalers or mechanical intervention for example oscillating positive expiratory device (OPEP), such as Aerobika®.

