4.5 Sample Size

[figure not shown]
According to Cohen's d formula, Cohen suggested that effect size of 0.2, 0.5 and 0.8 as small, medium and large effect size respectively. Effect sizes are the most important outcome at which the researchers want to know whether an intervention or experimental manipulation has an effect greater than zero, or (when it is obvious an effect exists) how big the effect is⁽⁴⁰⁾. In our study, we aim to have a medium effect size with the usage of Aerobika®. An effect size of 0.5 is described as medium and is 'large enough to be visible to the naked eye'⁽⁴¹⁾.

By using online statistical calculator apps; Sample Size Calculator for Comparing Paired Differences, this study would require a sample size of 34 to achieve a power of 80% and a level of significance of 5% for detecting an effect size of 0.5 paired differences (Dhand, N. K., & Khatkar, M. S. (2014). Statulator: An online statistical calculator. Sample Size Calculator for Comparing Two Paired Means. <http://statulator.com/SampleSize/ss2PM.html>.

Additional of 40% samples is recruited to avoid subject consent withdrawal, drop out, or missing data. Therefore, a total of minimum 48 patients will be recruited for this study. However, we aim to recruit 60 patients as we were sponsored 60 units of Aerobika® OPEP.

The outcomes of this study will be evaluated on all patients by comparing all the parameters during baseline and at 3- and 6-months follow-up after using Aerobika®. There will be no non-interventional arm as the sample size will become bigger. During the COVID-19 pandemic era, we would like to reduce the exposure towards those performing respiratory tests. The other limitations as well with larger sample size are budget and time constraint.

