4.6 Data Collection Pathway

4.7 Dummy Table

Table 1: Baseline demographic data

Variables	Study population (n=)	Stage 2	Stage 3	Stage 4	p -value
Age (mean +/- SD)					
Gender					
Male					
Female					
Ethnicity					
Malay					
Chinese					
Indian					
Others					
BMI (kg/m ²)					
COPD Duration					
Education					
Primary					
Secondary					
Tertiary					
Smoking status					
Yes					
No					
Comorbidities					

CHAPTER 5

RESEARCH ETHICS

Approval from the Research and Ethics Committee of Universiti Kebangsaan Malaysia Medical Centre (UKMMC) will be sought in order to commence the study. All the collected information will be strictly confidential and only accessible by the research team members. All patients will be kept anonymous and coded into the data collection sheet.

Participants will only be recruited in this study if informed consent was given, and will be allowed to withdraw from the study at any point. The research will be conducted according to standard of good clinical practice and the rights and safety of the participants are guaranteed throughout the study.

CHAPTER 6
FINANCIAL PLANS

Items	Justification	Quantity	Total (RM)
VOTE 27000: Research Items			
Microguard Bacterial Filter	Single use for every patient's test	RM 19.50 x 180 pcs	RM 3 510.00
Disposable Mouthpieces	Single use for every patient's test	RM 4.50 x 180 pcs	RM 810.00
Calibration Gas	Gas is used for operational standard for IOS and spirometry.	RM 4.50 x 180 pcs	RM 3 200.00
Total			RM 7 520.00
VOTE 29000: Professional Service (Perkhidmatan Ikhtisas)			
Honorarium for Respiratory Laboratory Technicians	Incentives for the involved respiratory unit technician who have expertise in handling the machines	RM 15 x 180 patients	RM 2 700.00
Total			RM 2 700.00
GRAND TOTAL			RM 10 220.00

CHAPTER 7
RESEARCH INFORMATION

CHAPTER 9
DATA COLLECTION SHEET

PATIENT'S STICKER

Name. :

Contact Number:

Age :

Gender :

Ethnicity :

Background Medical Problem:

- Diabetes Mellitus
- Hypertension
- Ischaemic heart Disease
- Heart Failure
- Previous stroke
- Dyslipidaemia
- Others:

.....
.....

Weight: Height: BMI:

First diagnosis of COPD: MMRC Class: COPD stage:

Number of exacerbations in the past 6 months :

Current COPD inhalers:

Inhaler technique:

Week:	0	12	24
CAT Score			
6MWT			
Exacerbation			
FEV ₁ (L predicted)			
FEV ₁ (%predicted)			
FEV ₁ /FVC (%)			
FEF 25-75 (L predicted)			
FEF 25-75 (% predicted)			
R20 (cm/H ₂ O/L/sec)			
R5 (cm/H ₂ O/L/sec)			

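### The inhaler rule covers changes after entry only: no criterion requires an unchanged regimen before baseline, so a late-emerging response to a recent change would be credited to the device

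*Combined protocol and SAP*

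**What the plan says.** The only inhaler rule among the criteria is item VII of section 4.2.5: "Change of inhaler during study period (will be dropped out from study". Section 4.3 adds that at clinic visits "his/her standard management for COPD will be checked to ensure no change in the inhaler regime". The same section ties the term to the patient's own follow-up: "Within the study period of 6 months, patient will be given follow-up phone calls every two to three weeks".

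On entry, item III of section 4.2.4 asks for "Stable COPD patients with mucus hyperproduction". The one time window attached to it, a month, concerns cough and sputum. Section 4.3 also restricts briefing and consent to patients who are stable, again without saying what that means for treatment. None of the seven inclusion and seven exclusion items mentions the inhaler regimen before baseline.

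The Chapter 9 data collection sheet has a line for "Current COPD inhalers", but none for when that regimen began or last changed.

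Section 4.5 explains the absence of a control group: "There will be no non-interventional arm as the sample size will become bigger". All outcomes are compared within patient, from baseline to 3 and 6 months.

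**The concern.** The plan already treats an inhaler change as serious enough to take a patient out of the study, but the rule looks forward only. Someone whose maintenance inhaler was changed a week before the baseline tests is on a constant regimen from then on, so the checks at weeks 12 and 24 find nothing.

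If the response to that change is still developing at baseline, the remainder appears in the change scores for IOS, CAT, spirometry and walking distance. A concurrent control group would carry the same drift and cancel it. Here nothing does, and the drift cannot be told apart from a device effect. At stake is the attribution of the primary result.

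**Working it through.** **1. Does the text close the gap?**

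- *Item VII.* It depends on what study period means. Section 4.3 uses it for six months per patient, and dropping out presupposes that the patient is already enrolled. On this reading a change before baseline is outside the rule.
- *The calendar reading.* Section 4.2.1 says "The study will be conducted from June 2021 to November 2022". Read that way, item VII would catch some changes made before enrolment, but not a change in May 2021 followed by enrolment in June 2021.
- *Stability.* An investigator might apply it to treatment, but nothing written requires this.
- *Visit checks.* They look for change after entry.

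The gap is therefore open on the more natural reading and only partly closed on the other.

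**2. The plan's own figure.** Section 4.5 gives n = 34 for a standardised paired difference of 0.5, 80% power and 5% significance. A two-sided paired t-test (noncentral t) gives power of 79.5% at n = 33 and 80.8% at n = 34, so 34 is reproduced. The same test is used below.

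**3. Size of the distortion.** Set the true device effect to zero. Let f be the share of patients with a recent inhaler change. Let δ be their mean post-baseline improvement from it, in within-group SDs of the paired difference. Neither value is in the documents; both are assumptions, with f from 5% to 30% and δ from 0.25 to 0.8. Then:

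- spurious mean change: f × δ
- SD of the mixture: √(1 + f(1 − f)δ²)
- noncentrality: √n × fδ / √(1 + f(1 − f)δ²)

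For f = 20%, δ = 0.5, n = 34: mean 0.20 × 0.5 = 0.10; SD √(1 + 0.16 × 0.25) = √1.04 = 1.020; noncentrality 5.831 × 0.10/1.020 = 0.57; chance of a significant improvement 8.0%.

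For f = 20%, δ = 0.8, n = 60: mean 0.16; SD √(1 + 0.16 × 0.64) = √1.1024 = 1.050; noncentrality 7.746 × 0.16/1.050 = 1.18; chance 21.2%.

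Chance of a significant result in the favourable direction (nominal 2.5%):

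| f | δ | Spurious mean (SD) | Share of the 0.5 target | n = 34 | n = 48 | n = 60 |
|---|---|---|---|---|---|---|
| 5% | 0.25 | 0.0125 | 2.5% | 2.9% | 3.0% | 3.1% |
| 10% | 0.5 | 0.05 | 10% | 4.6% | 5.2% | 5.7% |
| 20% | 0.5 | 0.10 | 20% | 8.0% | 9.8% | 11.3% |
| 20% | 0.8 | 0.16 | 32% | 13.6% | 17.7% | 21.2% |
| 30% | 0.8 | 0.24 | 48% | 24.7% | 33.3% | 40.4% |

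The 34, 48 and 60 are the section 4.5 figures for the calculated size, the recruitment minimum and the recruitment aim. The last column assumes that all 60 patients complete. A larger sample makes matters worse, because the bias stays fixed while the standard error shrinks.

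**The case against.** The strongest reply is that this is one of many before-after confounders in a study that openly explains why it has no control arm, and that its size rests on two assumed inputs. Both points stand. At f = 5% and δ = 0.25 the effect is negligible. The δ = 0.8 rows assume a residual inhaler response larger than the 0.5 effect the trial is sized to detect for the device. Only the part of the response that emerges after baseline matters: one already complete at baseline adds no bias, and the documents give no time course.

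Three stronger readings are tempting and are not supported:

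- *That recent changers could never be found afterwards.* Section 4.3 says clinical information is taken from the clerking chart and electronic record, and section 4.1 says the patients are already followed by this unit. The date may well be recoverable. What is missing is a plan to collect and use it.
- *That the bias always favours the device.* This holds for a beneficial step-up or switch. After a step-down or a poorly tolerated switch it could go the other way.
- *That the qualifying IOS itself prompts the switch.* Section 1.2 mentions targeted options once small airway disease is detected, "for example the use of small particle size inhalers or mechanical intervention", but presents them as alternatives. Section 4.3 describes a single IOS before the device. The Chapter 6 budget of 180 single-use filters equals 60 patients × 3 visits, which leaves none for a separate screening test. If the qualifying IOS is the baseline IOS, a switch it prompts comes after baseline, where item VII applies.

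The ambiguity of stable and study period also means that a careful investigator might decline a recent switcher. That is a reason to write the rule down, not evidence that it exists.

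**Conclusion.** The point holds as a gap in eligibility. The plan excludes inhaler changes after entry but not those shortly before baseline, and without a control arm any post-baseline response to such a change is counted as device effect. The gap itself rests on the text alone, taking study period in the sense that section 4.3 gives it.

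The size does not rest on the text. It depends on f and δ, which the documents do not give, and on the paired t-test implied by section 4.5. It runs from negligible when few patients changed recently to material at about 20% or more with a moderate residual response. No conclusion follows that the trial's result will be biased by any particular amount. The required sample of 34 is unaffected. The point warrants a change because the remedy is cheap and removes a confounder that the plan itself already treats as disqualifying.

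**What to change.** - **Eligibility (4.2.4).** Require the maintenance inhaler regimen to be unchanged for a stated period before the baseline IOS. Twelve weeks would match the first follow-up interval, but the investigators should set and justify the length. Defer recently switched patients and re-screen them once the period has passed.
- **Definition (4.2.5, item VII).** State that study period means the patient's own time from baseline to week 24.
- **Data (Chapter 9).** Add a field for the date of the last inhaler change, filled from the records already retrieved under section 4.3.
- **Analysis.** Pre-specify a sensitivity analysis of the primary outcome that excludes any recent changers who were enrolled.

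The cost is one eligibility line, one definition, one date field and one extra analysis. Recruitment slows slightly, with each recent switcher deferred for at most the chosen period. No extra test or visit is needed if the inhaler history is checked before baseline testing. With f = 0 the favourable-direction error from this source returns to 2.5%. The change does not cure the wider lack of a control arm.
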